#### **3.3.8.1 Clinical Dementia Rating-Sum of Boxes**

The Washington University CDR is a global assessment instrument that yields Global (GS) and Sum of Boxes (SB) scores. The CDR is derived from a semi-structured interview with the patient and an appropriate informant, and it rates impairment in six categories (memory, orientation, judgment and problem solving, community affairs, home and hobbies, and personal care) on a 5-point scale in which no impairment=0, questionable impairment=0.5, and mild, moderate, and severe impairment=1, 2, and 3, respectively. From the six individual category ratings or box scores the CDR-GS is established by clinical scoring rules where CDR 0=no dementia and CDR of 0.5, 1, 2, or 3=questionable, mild, moderate, or severe dementia, respectively ([Morris 1993](#)). The CDR-SB score is a detailed quantitative general index that provides more information than the CDR-GS in patients with prodromal to mild dementia ([O'Bryant et al. 2010](#)). In particular, the CDR-SB has been proposed for use in longitudinal assessment of dementia and is widely used in AD studies as a global measure of disease progression ([Lynch et al. 2006](#)). Furthermore, as proposed in the FDA's draft guidance for developing drugs for the early stages of disease, the use of a composite scale, validated in early stage patients to assess both cognition and function as a single primary efficacy outcome measure, is appropriate. The CDR-SB score fulfills these criteria ([FDA 2013](#)) and is now being utilized as the sole primary endpoint in studies of patient populations that encompass prodromal to mild AD including AMARANTH (<https://clinicaltrials.gov/ct2/show/NCT02245737>) and PRIME (<https://clinicaltrials.gov/ct2/show/NCT02477800>).

The proposal for the Phase III program is to employ the CDR-SB as a primary endpoint for an integrated functional/global assessment, *and the ADAS-Cog-13 and ADAS-Cog-11, ADCS-iADL and ADCS-ADL as key secondary endpoints to additionally support assessment of cognition as a core symptom of this disease (ADAS-Cog) and function (ADCS-ADL instrumental function subscore and total score), separately (see Section 3.3.9).*

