#### **3.3.9.1 Alzheimer's Disease Assessment Scale-Cognition**

The ADAS-Cog is an examiner-administered battery that assesses multiple cognitive domains, including memory, comprehension, praxis, orientation, and spontaneous speech (Rosen et al. 1984; Mohs et al. 1997). The ADAS-Cog is considered the standard primary endpoint in AD treatment studies (Mani 2004) and is generally considered the gold standard for assessing cognitive function in AD clinical studies (Cano et al. 2010; Sevigny et al. 2010). The 12-item version of the scale does not include adequate assessment of executive function particularly for patients in the early stages of AD. In the crenezumab Phase II program, the 12-item version (ADAS-Cog-12) was used in patients with mild to moderate AD (defined as screening MMSE score of 18–26), and a treatment effect was detected in a subpopulation of patients with mAD (MMSE, 22–26). Because of the expected increased sensitivity to detect a treatment effect in patients on the milder part of the AD continuum, the Sponsor proposes to use the 13-item version (ADAS-Cog-13), which is supplemented with executive measures sensitive to change in patients at the milder end of the disease spectrum (Mohs et al. 1997) as the key secondary endpoints.

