#### **4.6.5.2 Alzheimer's Disease Assessment Scale-Cognition**

The ADAS-Cog is the most frequently used scale to assess cognition in clinical trials for mild to moderate AD ([Rozzini et al. 2007](#); [Connor and Sabbagh 2008](#); [Ihl et al. 2012](#)). The modified version will be used; it has 13 items and includes the addition of 1) delayed word recall, and 2) number cancellation, as well as use of only one trial for word recognition. This is the version used in the Alzheimer's Disease Neuroimaging Initiative protocol (<http://www.adni-info.org/Scientists/ADNIStudyProcedures.html>). Equivalent alternate forms of the word recall, word recognition, and number cancellation subtests will be used in successive test administrations.

The 11-item version of ADAS-COG will also be analyzed.

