### **6.1 *DETERMINATION OF SAMPLE SIZE***

Determination of sample size is based on patients enrolled in the Global Enrollment Phase. In this study, 750 patients will be enrolled with 375 patients per treatment arm (crenezumab or placebo) during the Global Enrollment Phase. [REDACTED]

The estimate of sample size required to demonstrate efficacy with regard to CDR-SB is based on the following assumptions:

- The mean change in CDR-SB from baseline to Week 105 is 2.6 points in the placebo arm

- A common SD across treatment arms for change from baseline to Week 105 in CDR-SB of approximately 3.07 (this corresponds to a coefficient of variation of 118% for change in CDR-SB from baseline to Week 105 in a prodromal to mild AD population in the placebo arm)
- The dose level has a true effect of a 30% relative reduction in deterioration of CDR-SB
- 35% of randomized patients will dropout by Week 105

This sample size will have 80% power to detect a true treatment effect of 30% relative reduction in deterioration of CDR-SB at 2-sided  $\alpha$  of 0.05.

In the event that the rescue strategy or change in dose is required, the number of patients enrolled in the new dose group and its concurrently enrolled placebo arm will be 750 patients (375 patients per treatment arm) during the Global Enrollment Phase. All patients already enrolled on 60 mg/kg of *study treatment* and corresponding concurrently enrolled placebo patients will be replaced with new patients.

*A blinded assessment of the pooled standard deviation of CDR-SB change from baseline will be performed by the Sponsor at a specified timepoint prior to unblinding. As a result, the sample size may be increased from 750 up to 1126 patients (563 patients per arm). Further details will be described in the Statistical Analysis Plan (SAP). The sample size will not be reduced on the basis of this assessment. Other factors external to the study may also trigger a decision to increase sample size.*

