#### **6.4.2 Secondary Efficacy Endpoints**

The absolute change from baseline in the continuous secondary efficacy endpoints listed in Section 2 (including cognition endpoints, global endpoints, disease pathology biomarkers, and endpoints that measure other AD symptoms and effects) will be analyzed using an MMRM analysis model similar to that described above for the primary efficacy endpoint.

In order to protect the overall type I error rate for the study when incorporating the hypothesis testing of the primary endpoints and the key secondary endpoints into the analysis, the fixed sequence testing procedure ([Westfall and Krishen 2001](#)) will be used to adjust for multiple comparisons. These endpoints will be tested in the following order:

- 1) Change from baseline to Week 105 in CDR-SB
- 2) Change from baseline to Week 105 in ADAS-Cog-13 *and* ADAS-Cog-11

- 3) *Change from baseline to Week 105 in iADL*
- 4) *Change from baseline to Week 105 in ADCS-ADL total score*

The treatment difference in the primary endpoint (change from baseline to Week 105 in CDR-SB) will be tested at a 2-sided 5% overall significance level using the O'Brien–Fleming boundary. If this test result is statistically significant at either the interim or the final analysis, the treatment difference in change from baseline to Week 105 in ADAS-Cog-13 will be tested at a two-sided 5% significance level. If the treatment effect on ADAS-Cog-13 is statistically significant, the treatment effect on *ADCS-iADL total score* will be tested at a two-sided 5% significance level *and likewise for ADL if iADL is significant*. If any test result is not statistically significant, testing of the subsequent endpoints will not occur.

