## **9.6 PROTOCOL AMENDMENTS**

Any protocol amendments will be prepared by the Sponsor. Protocol amendments will be submitted to the IRB/EC and to regulatory authorities in accordance with local regulatory requirements.

Approval must be obtained from the IRB/EC and regulatory authorities (as locally required) before implementation of any changes, except for changes necessary to

eliminate an immediate hazard to patients or changes that involve logistical or administrative aspects only (e.g., change in Medical Monitor or contact information).

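### Section 6.4.2 lists ADAS-Cog-11 in step 2 of the fixed sequence, but the decision rule below the list tests and gates on ADAS-Cog-13 alone

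*Combined protocol and SAP*

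**What the plan says.** Section 6.4.2 of the protocol sets up a fixed sequence to protect the overall type I error across the primary and key secondary endpoints. Its numbered list runs CDR-SB, then "Change from baseline to Week 105 in ADAS-Cog-13 *and* ADAS-Cog-11" as one step, then iADL, then ADCS-ADL total score.

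The decision paragraph under the list names four tests: CDR-SB, ADAS-Cog-13, ADCS-iADL and ADCS-ADL. ADAS-Cog-13 gets a two-sided 5% level once CDR-SB is significant. The next gate reads "If the treatment effect on ADAS-Cog-13 is statistically significant, the treatment effect on" ADCS-iADL will be tested at two-sided 5%, with ADL to follow if iADL passes. The paragraph closes with "If any test result is not statistically significant, testing of the subsequent endpoints will not occur". ADAS-Cog-11 does not appear in it.

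Other sections bear on the status of ADAS-Cog-11:

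- Section 3.3.8.1 names "ADAS-Cog-13 and ADAS-Cog-11, ADCS-iADL and ADCS-ADL as key secondary endpoints".
- Section 3.3.9.1, the key secondary rationale, argues for one version only: "the Sponsor proposes to use the 13-item version (ADAS-Cog-13), which is supplemented with executive measures sensitive to change".
- Section 4.6.5.2 says "The 11-item version of ADAS-COG will also be analyzed", with no level or order.

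**The concern.** A fixed sequence controls error because each test has one place, one level and one stated consequence if it fails. Two scales joined by a conjunction in a single step, with no order and no rule on whether both or either must pass, do not supply that.

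Two outcomes are left open:

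1. **ADAS-Cog-13 passes and ADAS-Cog-11 misses.** The gate sentence sends testing on to iADL. If ADAS-Cog-11 is a step 2 test, as the list has it, the stop sentence ends testing before iADL and ADL.
2. **ADAS-Cog-11 is significant.** Nothing says whether this may be claimed as a confirmatory result.

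Unless the text is settled before unblinding, the reading could be chosen with the results in view. At stake are the confirmatory claims on ADAS-Cog-11, iADL and ADL.

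**Working it through.** **Which text governs.** The list and the paragraph stand in the same section, and neither is said to override the other. Section 3.3.8.1 favours including ADAS-Cog-11 among the error-controlled endpoints. Section 3.3.9.1 favours the 13-item version alone. Section 4.6.5.2 is neutral. The deferral of further detail to the SAP in Section 6.4.1 concerns the primary endpoint, and no SAP text in the documents resolves the point. The passages cannot be reconciled without choosing one.

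**Planned CDR-SB power (Section 6.1), used as the gate below.** The inputs are 375 per arm, 35% dropout, placebo change 2.6, 30% reduction and SD 3.07.

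- Completers per arm: 375 × 0.65 = 243.75.
- Difference: 0.30 × 2.6 = 0.78.
- Noncentrality: 0.78 / (3.07 × √(2/243.75)) = 2.80.
- Power: Φ(2.80 − 1.96) = 80.1%, which reproduces the stated 80%.

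**Set-up for the ADAS-Cog figures.** Test statistics are correlated normals with critical value 1.96 (two-sided 5%). Noncentrality is 2.80 for 80% power and 1.96 for 50%. The documents give no ADAS-Cog or iADL power and no correlations, so these are assumptions. Here r is the correlation between the two ADAS-Cog statistics, and q is the correlation of CDR-SB with each of them, taken from 0 to 0.6.

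- A: P(at least one scale rejects | neither has an effect) = 1 − P(|Z₁| < 1.96, |Z₂| < 1.96). This is the false-claim rate once CDR-SB has passed, if both scales were claimed side by side at an unadjusted 5%.
- B: P(13 rejects, 11 does not), 80% power each, ignoring the CDR-SB gate. This equals 0.80 − P(both reject).
- C: P(CDR-SB rejects, 13 rejects, 11 does not), 80% power on each, for q = 0 to 0.6.
- D: P(both scales reject), 80% power each, ignoring the CDR-SB gate.

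| r | A | B | C (q = 0 to 0.6) | D |
|---|---|---|---|---|
| 0.80 | 7.8% | 7.1% | 5.7% to 4.7% | 73% |
| 0.90 | 7.0% | 5.0% | 4.0% to 3.3% | 75% |
| 0.95 | 6.5% | 3.5% | 2.8% to 2.3% | 76% |
| 0.98 | 5.9% | 2.2% | 1.8% to 1.5% | 78% |

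With 50% power per scale and CDR-SB still at 80%, C becomes 8.2% to 8.8% at r = 0.80 and 2.6% to 2.7% at r = 0.98.

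**Trials that would lose an iADL claim.** A claim is lost only if iADL would also have passed. Take event C with iADL significant too, 80% power on all four tests, and iADL correlated q with the others. This gives 4.5% to 3.4% of all trials at r = 0.80 and 1.4% to 1.1% at r = 0.98.

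**Split alpha.** With 2.5% per scale, power on each falls from 80% to 71%.

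**Paragraph as written.** CDR-SB, ADAS-Cog-13, iADL and ADL, each at 5% and each gated on the one before, give 5% overall at a single analysis.

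**The case against.** The best reply is that the decision paragraph is the operative rule and is complete without ADAS-Cog-11. Every test it names has a level and a gate, it controls alpha, and the 11-item version can be read as supportive under Section 4.6.5.2. A SAP finalized before unblinding could also close the gap. The two versions share most of their items, so the higher correlations are the more plausible ones. At r = 0.95 to 0.98 and 80% power, the conflicting outcome arises in only about 2.8% to 1.5% of trials. The inflated error rates in column A need a side-by-side reading that no sentence states and that fits poorly with a declared fixed sequence.

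Much of this stands. The written four-endpoint path is workable, the practical frequency is low, and column A describes one possible reading, not the plan's error rate. But if the paragraph governs, the numbered list and Section 3.3.8.1 are wrong and still need correcting. The stop sentence does not rescue the rule, because it is the sentence that conflicts with the gate once ADAS-Cog-11 counts as a step 2 test. No text in the documents defers this point to the SAP.

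The amendment rationale says endpoints were added to the error-control hierarchy and that new text is in italics. In Section 6.4.2 the italics show the paragraph updated for iADL and ADL but not for ADAS-Cog-11. That does not establish intent, but it explains why a reader cannot tell omission from design.

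**Conclusion.** The concern holds. Section 6.4.2 gives two incompatible accounts of step 2 in a confirmatory procedure, and nothing else in the documents decides between them. The contradiction itself rests on no assumption. Its frequency does: the two accounts diverge in about 1.5% to 5.7% of all trials at 80% power per scale, or 2.6% to 8.8% at 50%, over r = 0.80 to 0.98. In about 1.1% to 4.5% (80% power on all four tests) an iADL claim depends on which account is followed. It should be fixed, but it is a key-secondary problem only: CDR-SB and its alpha are untouched.

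**What to change.** Before unblinding, make the list and the paragraph in Section 6.4.2 agree, and align Sections 3.3.8.1 and 3.3.9.1 in the same amendment. The simplest change keeps the ADAS-Cog-13 gate to iADL and takes ADAS-Cog-11 out of step 2:

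- **(a) Place it last.** The order becomes CDR-SB, ADAS-Cog-13, ADCS-iADL, ADCS-ADL total, ADAS-Cog-11, each at two-sided 5% and gated on the one before. The paragraph gains a clause that ADAS-Cog-11 is tested if ADL is significant. iADL and ADL are unaffected, but ADAS-Cog-11 can be claimed only if all four earlier tests pass.
- **(b) Label it supportive.** This gives up any confirmatory ADAS-Cog-11 claim and costs nothing else.

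If the sponsor wants ADAS-Cog-11 ahead of iADL, the paragraph must state the rule:

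- **(c)** its own step after ADAS-Cog-13;
- **(d)** both scales required to pass step 2;
- **(e)** alpha split between the scales, with the level then carried to iADL stated.

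Under (c) and (d) the text must also say that a miss on ADAS-Cog-11 stops iADL and ADL. The price is the divergence frequency given in the verdict, of which the iADL claims actually lost are the smaller share. Under (d), step 2 power falls from 80% to between 73% and 78%. Under (e) at 2.5% each, power per scale falls to 71%.

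The choice is the sponsor's. The cost is text in three sections, through the usual route in Section 9.6 ("Protocol amendments will be submitted to the IRB/EC and to regulatory authorities in accordance with local regulatory requirements"), with no extra data or patients.

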### **6.4.3 Exploratory Efficacy Analyses**

For time-to-event endpoints, the Kaplan–Meier method will be used to estimate the median time-to-event for each treatment arm. Cox proportional hazard model stratified by the randomization stratification factors will be used to estimate the hazard ratio and its 95% CI. The two-sided log-rank test, stratified by the randomization stratification factors, will be used to perform hypothesis testing for assessing treatment difference between the two treatment arms at a 5% significance level.

Subgroup *analyses of efficacy results may also be performed based on clinically relevant baseline factors. Subgroups will be defined by factors which may include one or more of the following: age, sex, race, dementia status (pAD vs. mAD), APOE $\epsilon$ 4 status, geographic region, use and non-use of background therapies for AD, or other clinically relevant factors at baseline.*

## **6.5 SAFETY ANALYSES**

The safety analysis population will include all randomized patients who received at least one dose of study drug, with patients grouped according to the treatment actually received.

- Incidence and nature of MRI safety findings: ARIA-E and ARIA-H
- Incidence, nature, and severity of serious adverse events
- Incidence, nature, and severity of adverse events
- Incidence of adverse events of special interest
- Incidence of treatment discontinuations due to adverse events
- Mean changes in clinical laboratory tests from baseline over time; incidence of treatment-emergent abnormal laboratory values and abnormal laboratory values reported as adverse events
- Mean change in ECG assessments from baseline over time and incidence of abnormal ECG assessments

- Incidence of immunogenicity as evidenced by antibodies to crenezumab or other components of drug product
- Physical and neurologic examination abnormalities
- Mean change in vital signs (blood pressure, heart rate) from baseline over time and incidence of abnormal vital sign measurements
- Changes in CSSR-S scores from baseline over time.

## **6.6 PHARMACOKINETIC ANALYSES**

Serum concentration data for crenezumab will be tabulated and summarized. Descriptive summary statistics will include the arithmetic mean, median, range, SD, and coefficient of variation, as appropriate. Since a sparse PK sampling design is being used, population (non-linear mixed-effects) modeling will be used to analyze the dose concentration-time data of crenezumab. Information from other clinical studies may be incorporated to establish the PK model. The influence of patient characteristics (e.g., demographics, disease stage) and background medication on the pharmacokinetics of crenezumab will be explored using the PK model. The selection of parameters and the derivation of individual measures of exposure, such as AUC,  $C_{max}$ , and trough serum concentration, will depend on the final PK model used for this analysis. The results of this modeling analysis may be reported separately from the clinical study report.

CSF concentrations data for crenezumab and the ratio between CSF and serum crenezumab will be tabulated and summarized as appropriate from the substudy (BN29553-CSF longitudinal).

## **6.7 BIOMARKER ANALYSES**

*Plasma Abeta concentrations and MRI-derived measurements over time, such as volumetric changes in whole brain, ventricles, hippocampus, or other structures, will be analyzed using the same methods used for the primary analysis. Brain amyloid load, brain tau load, and CSF markers of disease will be analyzed in their respective substudies (BN29552/BN29553-Amyloid PET longitudinal, BN29552/BN29553-tau PET longitudinal, and BN29553-CSF longitudinal). Further details can be found in the pertinent substudy protocol.*

Exploratory analyses of the relationship between crenezumab exposure and biomarker (imaging, plasma PD, CSF PD, or genetic), efficacy, or safety measures will be performed as appropriate. The results of these analyses may be reported separately from the clinical study report.

## 6.8 INTERIM ANALYSIS

Based on information that may emerge during the course of this study, the Sponsor may choose to conduct *one or more interim analyses*. *Interim analyses would be conducted by an independent data coordinating center and reviewed by iDMC. The Sponsor would remain blinded.* Interactions between the iDMC and Sponsor *would be carried out as specified in the iDMC Charter. The iDMC Charter would document potential recommendations the iDMC can make to the Sponsor as a result of the analyses (e.g., stop the study for futility).* *Below are further specifications in place to ensure the study continues to meet the highest standards of integrity should optional interim analyses be executed.*

*The Sponsor may choose to perform an optional futility analysis. No adjustment for multiple comparisons would be made to the  $\alpha$  level for this analysis, given that the decision rules for the futility analysis would not allow for the opportunity to stop the study early for overwhelming efficacy. At the time of a futility analysis, the threshold for declaring futility would be based on the probability of erroneously stopping the study being lower than a pre-specified level, when crenezumab has a true treatment effect on CDR-SB (false negative rate). If the observed treatment effect at the futility analysis is smaller than the derived threshold, the iDMC may recommend that the study be stopped for futility. Additional criteria for recommending that the study be stopped for futility may be added to the iDMC Charter.*

In addition, the Sponsor may perform an interim assessment for positive efficacy. The type I error rate will be controlled to ensure statistical validity is maintained. Specifically, the Lan-DeMets  $\alpha$ -spending function that approximates the O'Brien-Fleming boundary will be applied to determine the critical value for stopping for positive efficacy at the interim analysis (DeMets and Lan 1994). If the study continues beyond the interim analysis, the critical value at the final analysis would be adjusted accordingly to maintain the protocol-specified overall type I error rate, per standard Lan-DeMets methodology. Control of overall type I error in multiple comparisons of primary and key secondary endpoints are described in Section 6.4. This interim analysis *would also be reviewed by the iDMC, and the Sponsor would remain blinded.* Additional criteria for recommending that the study be stopped for positive efficacy may be added to the iDMC Charter.

*Further details (e.g., timing, data to be reviewed by the iDMC, thresholds, etc.) will be documented in the interim SAP. The interim SAP will be submitted to relevant health authorities at least 2 months prior to the conduct of an interim analysis.*

As information external to the study (e.g., from other compounds) becomes available during the conduct of the study, the Sponsor may implement changes to the protocol to incorporate such learnings into the study, if possible. Such learnings may be concerned with endpoints, biomarkers, and sample size reassessment due to the variability and size of treatment effect observed in other compounds, for example. The Sponsor could

implement such learnings through a protocol amendment while being blinded, but without consultation with the iDMC.

